11.1 Baseline and demographic data

To describe baseline and demographic data, preoperative, intraoperative and postoperative data will be summarized and compared between patients randomized to the CDR and RBDR groups. Binomial and categorical data will be described as number (N) and percentage. Continuous data will be analyzed for normality. Data will be tested for normality using the Shapiro-Wilk test. Normal data will be described by the mean and standard deviation; whereas, non-normal data will be described by the median and interquartile range. Nominal data will be compared with the Fischer's Exact test or the Chi-Square test, as appropriate. Normal continuous data will be compared with the 2-tailed, student t-test. Non-normal continuous data will be compared with the Mann-Whitney U test. All results with p<0.05 will be considered significant.

11.2 Primary Objective

To assess the primary objective, the number and percentage of patients in each group who have converted to NSR after 24 hours will be calculated. The number of patients who convert to NSR in each group will be compared with either the Fischer's Exact test or the Chi-Square test, as appropriate.

11.3 Secondary Objectives

To assess the secondary objectives, the following statistical analysis plan will be used:

- To compare the total time, in minutes, during the first 24 hours that the patient achieves target HR (HR < 110) between groups, first, the time that each patient has the target HR will be calculated. The total time at target HR will be calculated as the number of hourly HR measures ≤ 100 x 60 minutes. This calculated time data for each group will be will be analyzed for normality. Normal data will be described by the mean and standard deviation; whereas, non-normal data will be described by the median and interquartile range. If one group is normal and one group is non-normal, both groups will be reported as non-normal data. The total time at target HR between groups will then compared with either the 2-tailed, independent samples student t-test (normal data) or with the Mann-Whitney U test (non-normal data).

- To compare the time to achieve target HR (HR ≤ 110 bpm) between patients in each group, the time to achieve target HR will be calculated for each patient. This time will be calculated as the total time, in minutes, between the start of the initial amiodarone bolus and the first recorded HR ≤ 110 bpm. The time to achieve NSR data will be analyzed for normality. Normal data will be described by the mean and standard deviation, whereas

non-normal data will be described by the median and interquartile range. If one group is normal and one group is non-normal, both groups will be reported as non-normal data. The time to achieve NSR will then compared with either the 2-tailed, independent samples student t-test (normal data) or with the Mann-Whitney U test (non-normal data).

- To compare the time to achieve NSR between patients in each group, the time to achieve NSR will be calculated for each patient. For patients who do not convert to NSR by the time they are discharged from the hospital, the date/time that they achieve NSR will be the date/time of hospital discharge. The time to achieve NSR data will be analyzed for normality. Normal data will be described by the mean and standard deviation, whereas non-normal data will be described by the median and interquartile range. If one group is normal and one group is non-normal, both groups will be reported as non-normal data. The time to achieve NSR will then compared with either the 2-tailed, independent samples student t-test (normal data) or with the Mann-Whitney U test (non-normal data).
- To compare the percentage of patients who achieve NSR by ICU discharge and hospital discharge, the number of patients in each group who have converted to NSR at each time point will be calculated and reported as number and percentage. The number who have achieved NSR will be compared with the Fischer's Exact test or the Chi-Square test, as appropriate.
- To compare the percentage of patients who have recurrent AF before ICU discharge and hospital discharge, the number of AF episodes after the initial AF episode will be counted

for each patient in each group prior to ICU discharge and prior to hospital discharge. The mean (normal data) or median (non-normal data) number of additional AF episodes will be compared between the groups using the 2-tailed, independent samples student t-test (normal data) or with the Mann-Whitney U test (non-normal data).

- To compare the incidence and severity of hypotension, the number of patients who develop hypotension will first be calculated and reported as number and percentage. The number of patients with hypotension will be compared with the Fischer's Exact test or the Chi-Square test, as appropriate . The number of patients who develop mild, moderate, severe or very severe hypotension will then be calculated and reported as number and percentage. The number of patients with each severity class will then be compared between groups using Somers' D test for ordinal data.
- To compare the incidence and severity of conduction abnormalities, the number of patients who develop bradycardia will first be calculated and reported as number and percentage. The number of patients with bradycardia will be compared with the Fischer's Exact test or the Chi-Square test, as appropriate. The number of patients who develop mild, moderate, severe or very severe conduction abnormalities will then be calculated and reported as number and percentage. The number of patients with each severity class will then be compared between groups using Somers' D test for ordinal data.

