1. BACKGROUND

Atrial fibrillation (AF) is a common complication following cardiac surgery, occurring in approximately 33% of all patients after cardiac surgery. AF can sometimes cause a rapid ventricular rate (RVR), defined as a HR greater than 110 beats per minute (BPM). AF is typically characterized as either stable (systolic blood pressure (SBP) \geq 90 mmHg) or unstable (SBP <90 mmHg). Patients with unstable AF with or without RVR may require immediate electrical cardioversion to restore normal sinus rhythm (NSR) and an appropriate blood pressure; whereas, patients with stable AF frequently undergo medical therapy to either treat RVR or to restore NSR.

Amiodarone is a class III antiarrhythmic with beta-blocker activity that also blocks myocardial potassium, sodium and calcium channels. In stable AF, amiodarone is frequently given to control the HR and restore NSR after cardiac surgery. In this setting, amiodarone is commonly given as an initial intravenous (IV) bolus (150 mg IV) followed by a combined IV and oral load to a total dose of 8 gm. Because of amiodarone's beta-blocker activity, the IV bolus is associated with a reduced HR and may lead to restoration of NSR on its own. For this reason, some clinicians will provide up to 5 additional IV amiodarone boluses during the drug's loading period to treat RVR. Other clinicians will not specifically treat RVR in stable AF and will continue with the routine amiodarone IV and oral load. At this time, both dosing regimens are routinely used for patients after cardiac surgery, the decision to use one over the other is made based on clinician preference. It is not known whether the repeated amiodarone dosing regimen is better than the conventional amiodarone dosing regimen with regard to successful conversion to NSR or the time to conversion to NSR in patients with stable AF.

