3.2 Secondary Objectives

The secondary objectives of this study are:

- Compare the total time, in minutes, during the first 24 hours that the patient achieves target HR (HR < 110 bpm) between patients who receive a repeated amiodarone bolus dosing regimen and those who receive a conventional amiodarone bolus dosing regimen.
- Compare the time to achieve target HR (HR < 110 bpm) between patients who receive a repeated amiodarone bolus dosing regimen and those who receive a conventional amiodarone bolus dosing regimen.

- Compare the time to achieve NSR between patients who receive a repeated amiodarone bolus dosing regimen and those who receive a conventional amiodarone bolus dosing regimen.
- Compare the percentage of patients who achieve NSR by ICU discharge and hospital discharge between patients who receive a repeated amiodarone bolus dosing regimen and those who receive a conventional amiodarone bolus dosing regimen.
- Compare the percentage of patients who have recurrent AF before ICU discharge and before hospital discharge between who patients who receive a repeated amiodarone bolus dosing regimen and those who receive a conventional amiodarone bolus dosing regimen.
- Compare the incidence and severity of hypotension between patients who receive a repeated amiodarone bolus dosing regimen and those who receive a conventional amiodarone bolus dosing regimen.
- Compare the incidence and severity of conduction abnormalities between patients who receive a repeated amiodarone bolus dosing regimen and in those who receive a conventional amiodarone bolus dosing regimen.
- Compare the incidence and severity of amiodarone-related pulmonary fibrosis between patients who receive a repeated amiodarone bolus dosing regimen and those who receive a conventional amiodarone bolus dosing regimen.

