10.3 Postoperative data

- Date/time of ICU admission
- Date/time of extubation

- Date/time of ICU discharge
- Date/time of hospital discharge
- Vasopressor (norepinephrine, vasopressin) use at ICU admission
- Inotrope (dopamine, epinephrine, milrinone, dobutamine) use at ICU admission
- Pacemaker use at ICU admission
- Date/time of first AF
- Presence of rapid ventricular response with first AF
- Heart rate at time of AF diagnosis
- Heart rate at initiation of study group treatment (initial amiodarone bolus)
- Hourly heart rate for 24 hours, beginning at start of study group treatment
- Date/time of study randomization
- Date/time of first study drug administration
- Total number of amiodarone boluses administered
- Restoration of normal sinus rhythm by ICU discharge
- Restoration of normal sinus rhythm by hospital discharge
- Date/time of normal sinus rhythm
- Total number of stable AF episodes (excluding initial episode) prior to ICU discharge
- Total number of stable AF episodes (excluding initial episode) prior to hospital discharge
- Presence of hypotension (SBP < 90 mmHg or increase in vasopressor infusion by 1.5x to achieve SBP > 90 mmHg) after amiodarone therapy during amiodarone IV load period
- Severity of hypotension after amiodarone therapy during amiodarone IV load period
 - Mild: No intervention needed
 - Moderate: Hypotension resolved after fluid bolus

- Severe: Hypotension requiring vasopressor or inotropic therapy
- Very Severe: Hypotension requiring multiple vasopressor or inotropic therapies
- Presence of bradycardia (HR <60 beats per minute) after amiodarone therapy during amiodarone IV load period
- Presence of conduction abnormality during amiodarone IV load period
- Severity of conduction abnormality during amiodarone IV load period
 - Mild: No intervention
 - Moderate: Temporary pacemaker required for ≤ 12 hrs
 - Severe: Temporary pacemaker required for 12-48 hrs
 - Very Severe: Temporary pacemaker required for ≥ 48 hrs or permanent pacemaker required
- Presence of pulmonary fibrosis related to amiodarone therapy
- Severity of pulmonary fibrosis related to amiodarone therapy
 - Mild: No intervention needed
 - Moderate: Discharged on oxygen at night only
 - Severe: Discharged on continuous oxygen
 - Very Severe: Discharged on mechanical ventilation or patient death due to pulmonary fibrosis

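### Total time at target heart rate is defined as HR < 110 but scored by counting hourly readings ≤ 100, so readings of 101–109 meet the target and earn no minutes

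*Protocol*

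**What the plan says.** Protocol 3.2 sets the endpoint as the "total time, in minutes, during the first 24 hours that the patient achieves target HR (HR < 110 bpm"), compared between the two dosing regimens. The corresponding bullet in Protocol 11.3 begins with the same target: "To compare the total time, in minutes, during the first 24 hours that the patient achieves target HR (HR < 110) between groups". The scoring instruction that follows in that bullet reads: "The total time at target HR will be calculated as the number of hourly HR measures ≤ 100 x 60 minutes". SAP 1.3 carries the same bullet, with the same opening target and the same formula.

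The source data are listed in Protocol 10.3: "Hourly heart rate for 24 hours, beginning at start of study group treatment".

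The neighbouring endpoint, time to target HR, also has two forms. Protocol 3.2 says "Compare the time to achieve target HR (HR < 110 bpm) between patients", whereas Protocol 11.3 and SAP 1.3 measure from "the start of the initial amiodarone bolus and the first recorded HR ≤ 110 bpm".

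The Background section describes rapid ventricular rate as "defined as a HR greater than 110 beats per minute".

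**The concern.** One endpoint has two cut-offs within a single bullet. A programmer who follows the formula produces minutes at HR ≤ 100, and the results table labels them minutes at HR < 110. Anyone reading the result against the objective would be misled about what was measured.

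The two adjacent heart-rate endpoints would also use different targets under one name. A patient at 105 bpm would have reached target for the time-to-target endpoint while accumulating no time at target.

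The trial is open-label. If the conflict is still there at analysis, either cut-off can be defended from the text, and the choice could be made with the data in view.

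A smaller mismatch sits beside it: time to target is < 110 in the objective and ≤ 110 in the analysis. That affects only readings of exactly 110 and carries little weight.

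**Working it through.** The documents contain no figure that depends on this definition (no sample size was calculated), so there is nothing of theirs to reproduce. The check applies both rules to the same readings.

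**Inputs from the documents**

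| Item | Cut-off | Place |
|---|---|---|
| Total time at target, objective | < 110 | Protocol 3.2 |
| Total time at target, opening of analysis bullet | < 110 | Protocol 11.3, SAP 1.3 |
| Total time at target, scoring formula | ≤ 100 | Protocol 11.3, SAP 1.3 |
| Time to target, objective | < 110 | Protocol 3.2 |
| Time to target, analysis | ≤ 110 | Protocol 11.3, SAP 1.3 |
| Rapid ventricular rate | > 110 | Protocol 1 |
| Tachycardia in the repeated-bolus arm | ≥ 110 | Protocol 9.2 |

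The scoring formula is the only entry at 100.

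**Step 1: where the rules disagree.** Written score = 60 × (number of hourly readings ≤ 100). Score for the stated target = 60 × (number of hourly readings < 110). For whole-number readings they differ at exactly nine values, 101 to 109. Each such reading costs 60 minutes.

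**Step 2: bounds per patient.** Taking 24 hourly readings, the maximum score is 24 × 60 = 1,440 minutes.
- All 24 readings at 105: the written rule gives 0 × 60 = 0; the stated target gives 24 × 60 = 1,440.
- 4 readings at 120, 8 at 108, 12 at 95: the written rule gives 12 × 60 = 720; the stated target gives (8 + 12) × 60 = 1,200.

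The shortfall can lie anywhere from 0 to 1,440 minutes.

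**Step 3: illustrative average shortfall.** The documents give no heart-rate mean or SD, so this step is an assumption: hourly HR normal with mean m and SD s, recorded as whole numbers. Expected omitted minutes = 1,440 × [Φ((109.5 − m)/s) − Φ((100.5 − m)/s)].

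Worked case, m = 100, s = 15: Φ(0.633) = 0.7367 and Φ(0.033) = 0.5133. The two rules give 1,061 and 739 minutes, a shortfall of 322.

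| Mean | SD 10 | SD 15 | SD 20 |
|---|---|---|---|
| 75 | 7 | 49 | 85 |
| 90 | 175 | 209 | 194 |
| 100 | 445 | 322 | 249 |
| 105 | 500 | 340 | 256 |
| 110 | 445 | 322 | 249 |

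For means of 90–110 and SDs of 15–20 the range is 194–340 minutes. For means of 75–110 and SDs of 10–20 it is 7–500 minutes.

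**Step 4: effect on the between-arm difference.** Further assumption: one arm's mean is 5 bpm lower, and SD is 15 in both. The difference in expected minutes under cut-off c (100.5 or 109.5) is 1,440 × [Φ((c − (m − 5))/15) − Φ((c − m)/15)], where m is the higher mean.

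| Higher mean m | ≤ 100 rule | < 110 rule |
|---|---|---|
| 90 | 131 | 66 |
| 100 | 187 | 139 |
| 110 | 171 | 189 |
| 120 | 101 | 166 |

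At the lower means the ≤ 100 rule enlarges the contrast; at the higher means it shrinks it. The direction cannot be told from the documents.

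**The case against.** The strongest reply is that this is a one-digit typing slip whose intent is obvious. The fast-rate thresholds elsewhere are all at 110, the objective and the opening of the bullet both name the target, and an attentive statistician would query the 100. The endpoint is one of eight secondary objectives. The primary outcome and the rule for closing or extending the trial at 60 subjects do not use it. The scoring is identical in both arms, so an understated minute count is not in itself a biased treatment effect. The minute estimates in steps 3 and 4 rest wholly on assumed distributions, and the span of 7–500 shows how little those assumptions settle. The formula is also explicit, so the risk is a mislabelled result more than an open choice.

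Much of this stands as to weight. The impact is confined to one secondary endpoint, no bias towards either arm is shown, and the only magnitude that follows from the documents alone is 60 minutes per reading of 101–109.

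It does not remove the conflict. A slip in the operative formula still produces the wrong number if followed. A text-extraction error is an unlikely explanation, because the protocol and the SAP carry the same sentence. The explicitness of the formula does not settle the matter either, since the target stated in the same bullet is equally explicit.

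**Conclusion.** The concern holds, with high confidence, because it is a direct conflict in the text. Following the formula gives a wrong result for the endpoint as stated: readings of 101–109 are on target by definition and score nothing. The firm bound is 60 minutes per such reading, up to 1,440 minutes per patient if there are 24 readings. The figure of 194–340 minutes per patient, and the finding that the between-arm difference may grow or shrink, are illustrations under an assumed normal heart rate and, for the latter, an assumed 5 bpm shift.

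This should be fixed before analysis. It does not threaten the primary outcome. The < 110 versus ≤ 110 mismatch for time to target is real but minor.

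**What to change.** Before analysis, amend Protocol 11.3 and SAP 1.3 so that total time at target is 60 minutes times the number of hourly readings with HR < 110, and time to target runs to the first recorded HR < 110. Both then agree with Protocol 3.2. If 100 was the intended cut-off for total time, change Protocol 3.2 and the opening of the analysis bullet in both documents to say so, and give the reason. This concerns the analysis definition only and implies nothing about treatment thresholds.

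The cost is a wording change in two documents. Hourly heart rate is already collected under Protocol 10.3, so the score can be computed under either cut-off without new data.

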Patients in both groups will receive an amiodarone bolus of 150 mg IV over 10 minutes then a 24-hour amiodarone loading infusion (1 mg/min for 6 hours followed by 0.5 mg/min for 18 hours). After these infusions have been completed, patients in both groups will receive additional enteral (400 mg amiodarone oral or per tube three times daily or 2 times daily if the patient has gastrointestinal intolerance when taking the drug three times daily) or intravenous amiodarone (0.5 mg/min continuous infusion) to complete an 8-gm total amiodarone load. After the amiodarone load is completed, patients in both groups will receive maintenance amiodarone (200 mg amiodarone oral or per tube once daily). Further management of amiodarone dosing will be at the discretion of the attending cardiac surgeon, critical care medicine specialist or cardiologist. Other medications will be at the discretion of the attending cardiac surgeon, critical care medicine specialist or cardiologist. Patients will be monitored continuously throughout the 24-hour amiodarone IV load time period according to standard protocol.

9.1 Conventional Dosing Regimen (CDR)

Patients randomized to the CDR group will receive the previously-described amiodarone bolus followed by a 1.0 mg/min IV amiodarone infusion for 6 hours and then a 0.5 mg/min IV amiodarone infusion for 18 hours.

9.2 Repeated Bolus Dosing Regimen (RBDR)

Patients randomized to the RBDR group will receive the previously-described amiodarone bolus followed by a 1.0 mg/min IV amiodarone infusion for 6 hours and then a 0.5 mg/min IV amiodarone infusion for 18 hours. In addition, patients in the RBDR will receive an additional 150 mg IV amiodarone bolus whenever the patient develops tachycardia (Heart Rate (HR) \geq 110 beats per minute) lasting more than 10 minutes. This bolus may be repeated up to a total of 5 times (6 total boluses) over the first 24 hours.

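### Minutes at target heart rate is a count of hourly readings with no denominator, so each missing reading is scored as 60 minutes off target; whether the time-zero reading counts is left open

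*Protocol*

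**What the plan says.** Protocol 3.2 lists this objective first among the secondary objectives: "Compare the total time, in minutes, during the first 24 hours that the patient achieves target HR (HR < 110 bpm"), by regimen. Target is set by an upper limit only.

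Protocol 11.3 gives the calculation, and SAP 1.3 repeats it word for word: "The total time at target HR will be calculated as the number of hourly HR measures" at or below 100, multiplied by 60 minutes. The totals are then compared by t-test or Mann-Whitney U test, depending on normality.

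The source data are defined in Protocol 10.3: "Hourly heart rate for 24 hours, beginning at start of study group treatment". The same list has a separate item for heart rate at the initial amiodarone bolus. It does not give the number of hourly readings, and does not say whether the value at the bolus is also the first of the hourly series.

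Neither document says what to do when an hourly reading is missing, or when a patient dies or withdraws before 24 hours.

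**The concern.** The objective is a duration within a fixed 24-hour window. The formula turns readings into minutes by giving each qualifying reading 60 minutes, but it never refers to how many readings exist. It equals time at target only if every patient has exactly one reading for each of 24 hours. When a reading is absent, the analyst who follows the formula assigns failure to that hour without the plan having said so.

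This can matter for the comparison as well as for the individual score. The trial is open-label (Protocol 4), and only the repeated-bolus arm has an action triggered by sustained tachycardia (Protocol 9.2), so equal completeness of charting cannot simply be assumed. A series cut short by death or withdrawal is scored in the same way as uncontrolled rate.

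The second issue is which readings belong to the series. A value at the moment treatment starts cannot reflect the assigned regimen. It can still be at target, because randomization requires persistent stable AF after up to 15 mg IV metoprolol and 20 minutes of observation (Protocol 9), not a heart rate above the target.

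**Working it through.** The documents give no expected value, power or result for this endpoint, so there is no stated figure to reproduce. The check applies the formula to simple illustrative series. All heart rates described as at target are 98 or lower, and the off-target one is 130, so the results do not depend on which of the plan's cut-offs is used.

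**Inputs.** Window: 24 h x 60 = 1,440 minutes (Protocol 3.2). Rule as written: 60 x number of readings at target (Protocol 11.3, SAP 1.3). Rule for comparison: 1,440 x (readings at target / readings recorded).

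**1. Missing readings, with every recorded reading at target (90 bpm), 24 due**

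| Missing | Recorded | As written | Scaled to recorded |
|---|---|---|---|
| 0 | 24 | 24 x 60 = 1,440 | 1,440 |
| 1 | 23 | 23 x 60 = 1,380 | 1,440 |
| 2 | 22 | 22 x 60 = 1,320 | 1,440 |
| 4 | 20 | 20 x 60 = 1,200 | 1,440 |
| 6 | 18 | 18 x 60 = 1,080 | 1,440 |

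**2. Where the written rule sits among the possible values.** Take 20 recorded, of which 15 are at target. As written: 15 x 60 = 900. If all four missing hours were in fact at target: 19 x 60 = 1,140. If none were: 900. Scaled: 1,440 x 15/20 = 1,080. The raw count always takes the lowest value compatible with the data. Scaling gives a value inside the range, and reaches its upper end when all recorded readings are at target, as in step 1.

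**3. Effect on the comparison.** Let *d* be the difference between arms in mean number of missing readings, and *p* the share of unrecorded hours truly at target. Neither is given in the documents; both are assumptions. The difference in means shifts by 60 x *p* x *d* minutes. For *d* = 1 this is 30 minutes at *p* = 0.5 and 60 at *p* = 1; for *d* = 2 it is 60 and 120. For *d* = 0 with equal *p*, the arms are lowered equally and there is no shift.

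**4. Time-zero reading, under the three indexings the text allows**

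| Series | Hours 0-23 | Hours 1-24 | Hours 0-24 |
|---|---|---|---|
| 130 at hour 0, then 95 | 23 x 60 = 1,380 | 1,440 | 24 x 60 = 1,440 |
| 98 at hour 0, then 95 | 1,440 | 1,440 | 25 x 60 = 1,500 |

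The time-zero value changes the score by at most 60 minutes, or 60/1,440 = 4.2% of the window. Only the 25-reading indexing can exceed 1,440.

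**The case against.** **Gaps may be few.** Protocol 9 says "Patients will be monitored continuously throughout the 24-hour amiodarone IV load time period according to standard protocol", and nothing in the documents suggests frequent or arm-related gaps. That stands as a limit on the likely size. It does not supply a rule: continuous monitoring is not the same as a complete set of recorded hourly values, and early death or withdrawal ends the series however well it was charted.

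**The formula is not a written imputation rule.** True. Scoring a gap as failure is an unstated consequence of the arithmetic, which is why the plan should decide it openly.

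**Scaling has its own weakness.** It assumes the gaps are uninformative, and without a floor a single recorded reading at target would earn 1,440 x 1/1 = 1,440 minutes. Both points stand, and are why the fix needs a minimum number of readings and a rule for death and withdrawal.

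**Readings at hours 0 to 23 are coherent,** with each standing for the hour that follows and a maximum of 1,440. This also stands. A reader might infer that the plan takes 25 readings and allows 1,500 minutes in a day; the documents do not say so. Hourly values over 24 hours can equally mean 24 readings, and the heart rate at the bolus is a separate item never said to enter the count. A time-zero reading, if counted, falls under the same rule in both randomized arms, so systematic favouring of one arm does not follow.

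**A reader might also infer that bradycardia is being booked as efficacy,** because hours below 60 bpm count as at target. The documents do not support treating this as a fault. The objective defines target by an upper limit only, so these hours are what it sets out to count. Protocol 10.3 records bradycardia separately, and under the conduction-abnormality objective in 11.3, "the number of patients who develop bradycardia will first be calculated and reported as number and percentage" and then tested between arms. Removing such hours would redefine a clinical target, and would score a patient in sinus rhythm at 58 bpm all day as 0 minutes, the same as one at 140 bpm throughout.

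**Conclusion.** The missing-reading defect holds. Following the formula as written gives the lowest score compatible with the data whenever a reading is absent, understating time at target by up to 60 minutes per gap (240 minutes in the 20-of-24 example, if the missing hours resembled the recorded ones). Whether this distorts the comparison depends on how completeness differs between arms, which the documents do not tell us.

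The time-zero issue holds as an ambiguity only. The literal reading of Protocol 10.3 includes such a value, but the indexing is not fixed. At stake are at most 60 minutes per patient, unrelated to treatment and under the same rule in both arms.

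This concerns a secondary endpoint and does not touch the primary analysis. It should be corrected before the data are analysed.

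**What to change.** In Protocol 11.3 and SAP 1.3:

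- Score the 24 readings after the start of treatment, at hours 1 to 24, and say that the time-zero reading is descriptive only.
- Define minutes at target as 1,440 x (readings at target / readings recorded).
- Report the number of recorded readings by arm.
- State a minimum number of readings for a patient to be scored, and how death or withdrawal within 24 hours is handled.
- Keep the raw count x 60 as a sensitivity analysis.

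Do not add a lower heart-rate limit to the target. Minutes with a heart rate below 60 may be shown as an optional descriptive row.

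Separately, the target cut-offs must be reconciled: below 110 in Protocol 3.2 and at the start of the bullet in Protocol 11.3 and SAP 1.3, at or below 100 in the formula itself, and at or below 110 in the next bullet. The changes above are needed whichever cut-off is kept.

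The cost is wording and one sensitivity analysis on data already collected. The small downside is the assumption that gaps are uninformative, which the by-arm counts and the raw-count analysis let a reader judge.
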